### 3.2. Secondary Endpoints

The secondary objective will be evaluated by the following endpoints:

- The GM values of SARS-CoV-2 S protein-specific bAb on Day 1, Day 57 (1 month after Dose 2), Day 209 (6 months after Dose 2), Day 394 (1 year after Dose 2), BD-Day 1 (at least 3 months or 6 months after Dose 2), BD-Day 29 (1 month after mRNA-1273 booster dose or third dose), BD-Day 181 (6 months after mRNA-1273 booster dose or third dose), and BD-Day 366 (1 year after mRNA-1273 booster dose or third dose).
- The GM values of SARS-CoV-2-specific nAb on Day 1, Day 57 (1 month after Dose 2), Day 209 (6 months after Dose 2), Day 394 (1 year after Dose 2), BD-Day 1 (at least 3 months or 6 months after Dose 2), BD-Day 29 (1 month after mRNA-1273 booster dose or third dose), BD-Day 181 (6 months after mRNA-1273 booster dose or third dose), and BD-Day 366 (1 year after mRNA-1273 booster dose or third dose).
- The incidence of SARS-CoV-2 infection including symptomatic and asymptomatic infection (by serology and/or RT-PCR), starting 14 days after the second dose of IP, and starting 14 days after the first dose of IP. SARS-CoV-2 infection will be defined in participants with negative SARS-CoV-2 at baseline:
  - bAb level against SARS-CoV-2 nucleocapsid protein negative at Day 1 that becomes positive (as measured by Roche Elecsys) post baseline, OR
  - Positive RT-PCR post baseline.
- The incidence of SARS-CoV-2 infection measured by RT-PCR and/or bAb levels against SARS-CoV-2 nucleocapsid protein (by Roche Elecsys) post baseline in participants with negative SARS-CoV-2 at baseline, in the absence of any COVID19 symptoms, starting 14 days after the second dose of IP, and starting 14 days after the first dose of IP

- The incidence of the first occurrence of CDC Case Definition of COVID-19 post baseline, starting 14 days after the second dose of IP, and starting 14 days after the first dose of IP. COVID-19 is defined as symptomatic disease based on the following criteria according to CDC case definition:
  - The participant must have a positive test for SARS-CoV-2 by RT-PCR; AND
  - Either
    - The participant must have experienced at least ONE of the following systemic symptoms: Fever (temperature  $\geq 38^{\circ}\text{C}/\geq 100.4^{\circ}\text{F}$ ) or chills (of any duration, including  $\leq 48$  hours), fatigue, headache, myalgia, nasal congestion or rhinorrhea, new loss of taste or smell, sore throat, abdominal pain, diarrhea, nausea/vomiting, poor appetite/poor feeding; OR
    - The participant must have experienced at least ONE of the following respiratory signs/symptoms: cough (of any duration, including  $\leq 48$  hours), shortness of breath or difficulty breathing (of any duration, including  $\leq 48$  hours)
- The incidence of the first occurrence of the P301 primary definition of COVID-19 case post baseline, starting 14 days after the second dose of IP, and starting 14 days after the first dose of IP.

The alternative case definition of COVID-19 is defined by the following criteria:

- The participant must have experienced at least TWO of the following systemic symptoms: Fever ( $\geq 38^{\circ}\text{C}/\geq 100.4^{\circ}\text{F}$ ), chills, myalgia, headache, sore throat, new olfactory and taste disorder(s), OR
- The participant must have experienced at least ONE of the following respiratory signs/symptoms: cough, shortness of breath or difficulty breathing, OR clinical or radiographical evidence of pneumonia; AND
- At least one positive RT-PCR test for SARS-CoV-2

### 3.3. Exploratory Endpoints

The exploratory endpoints are the following:

- Alignment of genetic sequence of viral isolates with that of the vaccine sequence
- Relative amounts or profiles of S protein-specific bAb and specific nAb values in serum
- Description of clinical severity and immune responses of participants who are identified as infected by SARS-CoV-2 (COVID-19)
- Magnitude, phenotype, and percentage of cytokine-producing S protein-specific T cells, as measured by flow cytometry at different time points after vaccination relative to baseline
- GM and GMFR of bAb levels against SARS-CoV-2 nucleocapsid protein (quantitative IgG)
- GM, SRR, and GMFR of Ab against variant(s) of concern or interest

#### 4. Study Design

##### 4.1. Overall Study Design

This is a Phase 2/3, three-part, open-label, dose-escalation, age de-escalation and randomized, observer-blind, placebo-controlled, expansion study intended to infer the effectiveness of mRNA-1273 in children aged 6 months to < 12 years. The study population will be divided into 3 age groups (6 years to < 12 years, 2 years to < 6 years, and 6 months to < 2 years) and up to 3 dose levels (25, 50, and 100 µg) of mRNA-1273 will be evaluated (and a third dose or an optional booster of 10 or 25 µg).

The study will be conducted in 3 parts. Part 1 of the study will be open label and consist of dose-escalation, age de-escalation in 1,275 participants (see Table1 below for the number of participants in each age group) to select the dose for each age group. Part 2 of the study will be placebo-controlled, observer-blind evaluation of the selected dose in up to 12,000 participants (up to 4,000 participants each in the 6 years to < 12 years, 2 years to < 6 years, and the 6 months to < 2 years of age groups). Part 3 will be an open-label alternative dosing assessment in approximately 300 participants in the 6 years to < 12 years old age group to assess reactogenicity and immunogenicity of a lower dose regimen. No participants in Part 1 will participate in Part 2 or Part 3 of the study, and no participant in Part 2 will participate in Part 3 of the study.

**Table 1: Planned Age Groups and mRNA-1273 Dose Levels in Part 1 and Part 2, and Part 3 of the Study**

| Age Group             | Part 1                        |                     |                     | Part 2  |                              | mRNA-1273
25 µg
2 doses of
primary
series +a third
dose
(Month 0, 1,
5) |
|-----------------------|-------------------------------|---------------------|---------------------|---|------------------------------|--|
|                       | mRNA-1273
25 µg            | mRNA-1273
50 µg  | mRNA-1273
100 µg | Selected Dose
Level of mRNA-1273 From Part 1 | Placebo                      |  |
| 6 years to < 12 years |                               | Study Arm 1 (n=375) | Study Arm 2 (n=375) | Study Arm 8 (n=3,000)                           | Study Arm 9 (n=1,000)        | Study Arm 14 (n= approximately 300)  |
| 2 years to < 6 years  | Study Arm 7 (Optional) (n=75) | Study Arm 3 (n=75)  | Study Arm 4 (n=75)  | Study Arm 10 (n=up to 3,000)                    | Study Arm 11 (n=up to 1,000) |  |
| 6 months to < 2 years | Study Arm 5 (n=150)           | Study Arm 6 (n=150) |                     | Study Arm 12 (n=up to 3,000)                    | Study Arm 13 (n=up to 1,000) |  |

Note: mRNA = messenger RNA.

1. Four months post-Dose 2  $\pm$  28 days (at least 3 months and up to 5 months after Dose 2)

The study will begin with the oldest age group (6 years to < 12 years) and age de-escalate. Each age group will begin with Part 1 and may advance to Part 2 and Part 3 independently. The mRNA-1273 investigational vaccine or placebo will be administered as 2 intramuscular (IM) injections, approximately 28 days apart for Part 1 and Part 2. For Part 3, the mRNA-1273 investigational vaccine will be administered as 3 IM injections approximately 28 days apart for the 2 doses of primary series followed by a third dose at least 3 months and up to 5 months after receipt of the second dose of the primary series. The mRNA-1273 dose levels that will be evaluated in each age group in Part 1, Part 2 and Part 3 of the study are given in Table 1.

#### 4.1.1. Part 1, the Open-Label Phase

Part 1 of the study will be open label, dose-escalation and age de-escalation. The study schematic is presented in Figure 1.

The study will include 3 age groups: Group 1 with 750 participants ( $\geq$  6 years to < 12 years old) and Group 2 with approximately 225 participants ( $\geq$  2 years to < 6 years old) and Group 3 with 300 participants ( $\geq$  6 months to < 2 years old). Up to three dose levels (25 µg, 50 µg and 100 µg) will be evaluated in each age group in Part 1. Each age group will begin dosing

with the lowest dose planned for that group. Dose escalation and age de-escalation will progress only after confirming the safety of a dose level in each group after each IP injection.

The study will be initiated with enrollment of 375 participants in the 6 years to < 12 years age group (Study Arm 1), and dosing with 50 µg of mRNA-1273.

After at least 75 participants in Study Arm 1 have completed Day 8 (1 week after Dose 1 of mRNA-1273 50 µg), an internal safety team (IST) will review the available safety data and provide a recommendation whether to escalate the dose to 100 µg in the 6 years to < 12 years age group (Study Arm 2; n = 375) and independently whether to begin dosing at the 50 µg dose level in the 2 years to < 6 years age group (Study Arm 3; n = 75). After at least 75 participants in Study Arm 1 reach Day 36 (1 week after Dose 2 of mRNA-1273 50 µg), the IST will again review the available safety data and provide a recommendation whether to administer Dose 2 of mRNA-1273 100 µg in Study Arm 2 and whether to administer Dose 2 of mRNA-1273 50 µg in Study Arm 3. Simultaneously, the enrollment of the remaining 300 planned participants for both Arms 1 and 2 will be ongoing. A preliminary safety and immunogenicity data review of Arm 1, and Arm 2 as applicable, will aid in the selection of a dose level for Part 2. Once all or a subset of participants from each of Study Arms 1 and 2 reach Day 57 (1 month after Dose 2 of mRNA-1273), an interim analysis may be conducted to review the safety and immunogenicity data. Cumulative safety data for approximately 300 participants at the selected dose level will be reviewed by the Data Safety Monitoring Board (DSMB) before enrollment in Part 2, and the DSMB safety review recommendation will enable the expansion of the 6 years to < 12 years age group (Part 2) to receive either mRNA-1273 at the selected dose level (Study Arm 8; n = 3,000) or placebo (Study Arm 9; n = 1,000).

[figure not shown]
Similar analysis as above will apply to other age groups in part 1, details can be found in protocol section 3.1. An optional Arm 7 may be enrolled in middle age group (2 years to < 6 years, approximately 75 participants) at the 25 µg dose if the 100 µg dose is eliminated at any point during dose escalation process, to maintain dose ranging for this age group. A preliminary safety and immunogenicity data review of all applicable Arms will aid in the selection of a dose level for Part 2. Once all or a subset of participants in all applicable Arms reach Day 57 (1 month after Dose 2 of mRNA-1273), an interim analysis may be conducted to review safety and immunogenicity data. A preliminary safety and immunogenicity data review of all applicable Arms will aid in the selection of a dose level for Part 2 and for expansion of the 2 years to < 6 years age group (Part 2) to receive either mRNA-1273 at the

selected dose level (Study Arm 10; n = up to 3,000) or placebo (Study Arm 11; n = up to 1,000).

Once all participants in Study Arms 5 and 6 reach Day 57 (1 month after Dose 2 of mRNA-1273), an interim analysis may be conducted to review the tolerability and immunogenicity data at each dose level. A preliminary safety and immunogenicity data review of Arm 5 and Arm 6, as applicable, will aid in the selection of a dose level for Part 2 and allow for expansion of the 6 months to < 2 years age group (Part 2) to receive either mRNA-1273 at the selected dose level (Study Arm 12; n = up to 3,000) or placebo (Study Arm 13; n = up to 1,000). Detailed schematic of study arms and process can be found in Section 3.1 from protocol and Figure 1 below.

In general, if a decision is made not to proceed with administration of the higher dose and/or the second injection at a given dose level (eg, due to safety concerns), the participants scheduled to receive the higher dose may receive a lower dose, and the participants who had received the higher dose level as their first injection will likely be given the next lower dose level that was tolerated for their second injection. The dose level not tolerated in the older age group will not be administered in any of the younger age groups. Within an age group, if one of the dose levels is found to have an unacceptable tolerability profile, the age group may progress to Part 2 at a lower dose level.

[figure not shown]
**Figure 1 Study Design Schematic, Part 1: Dose-escalation, age de-escalation**

#### 4.1.2. Part 2, the Blinded Phase

The blinded phase of the study will be a placebo-controlled observer-blind evaluation of the selected dose in up to 12,000 participants (up to 4,000 participants each in the 6 years to < 12 years, 2 years to < 6 years, and the 6 months to < 2 years of age groups). No participants in Part 1 will participate in Part 2 of the study. Each age group will begin with Part 1 and advance to Part 2 independently. For each age group, the primary analysis immunogenicity in part 2 will be conducted after the pre-specified Immunogenicity Subset of participants reaches Day 57, and safety analysis will be conducted after a subset or all participants reach Day 57.

**Figure 2 Study Design Schematic, Part 2: Expansion**

Abbreviations: CMI = cell-mediated immunity; D = Day; S = spike; VTEU = Vaccine and Treatment Evaluation Units.

\*Expansion and primary analysis for each age group may occur at different times.

§Participants in each age group will be assigned to one of 5 phlebotomy cohorts. Participants in 3 of these 5 cohorts will provide blood specimens for immunogenicity on D1 (prior to randomization and first dose), D57, and one of D29 (prior to the second dose), D209, or D394 (such that each participant provides a total of 3 blood samples only). Participants in the Cohort D (remainder of the age group) will provide a blood sample on D1 (prior to randomization and before the first dose) and within 4 days of receiving Dose 2 at D30 (+3 days) for storage and potential future biomarker testing. A fifth cohort of participants (selected VTEU sites only) will provide blood samples for assessment of exploratory serology and CMI (S protein-specific T-cell responses) on D1 (prior to randomization and before the first dose), D43, D209, and D394.

#### 4.1.3. Optional Booster Doses

Per Amendment 7, Part 1 (all ages) and 6 years to < 12 years Part 2 participants will be offered an optional booster dose lower than the chosen primary series for each age group at least 6 months after Dose 2 of mRNA-1273 (Part 1 participants and Part 2 participants in Study Arm 8; Part 2 placebo recipients from Study Arms 9, who crossed over to mRNA-1273 after unblinding).

In Amendment 9, all participants in all age groups in Part 1 and Part 2 who have not yet received a booster dose will be offered a booster dose with mRNA-1273.214 (instead of mRNA-1273).

#### Optional Booster Doses for Part 1 and Part 2 Participants

[figure not shown]
| Age at Time of Booster | Booster dose
(mRNA-1273 or mRNA-1273.214) |
|------------------------|--|
|------------------------|--|

|                       |       |
|-----------------------|-------|
| 6 years to < 12 years | 25 µg |
| 2 years to < 6 years  | 10 µg |
| 6 months to < 2 years | 10 µg |

#### 4.1.4. Part 3, the Open-Label Phase (Alternative Dosing Assessment)

Part 3 of the study will be open-label. A total of approximately 300 participants in the 6 years to < 12 years old age group will be enrolled to receive 3 total doses of mRNA-1273 at 25 µg given as the primary series doses at Day 1 and Day 29 followed by a third dose at Day 149/booster dose (BD)-Day 1 (at least 3 months and up to 5 months after the second dose in the primary series). The primary analysis of immunogenicity and safety in Part 3 for Study Arm 14 will be conducted after all treated participants reach Day 57 (for primary series). The primary analysis of immunogenicity and safety for the third dose will be conducted after all participants who received a third dose reach Day 177/BD-Day 29.

#### Figure 3 Study Design Schematic, Part 3

#### 4.2. Sample Size and Power

The initial age groups in Part 1 are for estimation purposes. With approximately 750 participants (approximately 375 participants at each dose level of mRNA-1273) in the initial 6 years to < 12 years age group, there is at least a 90% probability to observe at least 1 participant with an AE at a true AE rate of 1% for a given dose level. In each of the younger age groups (2 years to < 6 years and 6 months to < 2 years), the safety assessment will occur during the conduct of Part 2 after approximately 375 participants have been exposed to mRNA-1273 at the dose level selected for Part 2. For further details, please refer to protocol section 7.5.2.

The sample size in the expansion (Part 2) is considered to be sufficient to support a safety database in the pediatric participants 6 months to < 12 years of age. With up to 3,000

participants each in the 6 years to < 12 years, 2 years to < 6 years, and 6 months to < 2 years of age groups exposed to mRNA-1273 at a given dose level in Part 2, the study has at least a 95% probability to observe at least 1 participant with an AE at a true 0.1% AE rate for a given dose level.

The planned sample size in the lower dosing assessment (Part 3) is approximately 300 children 6 years to < 12 years of age receiving mRNA-1273 25 µg. There is at least a 90% probability to observe at least 1 participant with an AE at a true AE rate of 1% in this group.

A subset of Full Analysis Set (FAS) participants (Immunogenicity Subset) in each age group will be selected for measuring immunogenicity data. The immunogenicity samples of the Immunogenicity Subset will be processed, and the analysis of primary immunogenicity endpoint will be based on the PP Immunogenicity Subset.

If a threshold of protection is available, for the primary immunogenicity endpoint, with approximately 289 participants on mRNA-1273 in the PP Immunogenicity Subset of an age group, there will be at least 90% power to rule out 70% with a 2-sided 95% CI (lower bound of the 95% CI > 70%) for the percentage of mRNA-1273 participants exceeding the accepted threshold if the true rate of participants exceeding the threshold is 80%.

If an acceptable antibody threshold of protection against COVID-19 is not available at the time of analysis for the primary immunogenicity endpoint, noninferiority tests of the 2 null hypotheses based on the 2 coprimary endpoints will be performed, respectively. The sample size calculation for each of the 2 noninferiority tests was performed, and the larger sample size was chosen for the study.

- With approximately 289 participants receiving mRNA-1273 in the PP Immunogenicity Subset of each age group in Study P204 and young adults ( $\geq 18$  to 25 years of age) in Study P301, there will be a 90% power to demonstrate noninferiority of the immune response, as measured by the antibody GM value, in pediatric population at a 2-sided alpha of 0.05, compared with that in young adults ( $\geq 18$  to 25 years of age) in Study P301 receiving mRNA-1273, assuming an underlying GMR value of 1, a noninferiority margin of 1.5 (lower bound > 0.667), and a point estimate minimum threshold of 0.8. The standard deviation of the natural log-transformed levels is assumed to be 1.5.
- With approximately 289 participants receiving mRNA-1273 in the PP Immunogenicity Subset of each age group in Study P204 and young adults ( $\geq 18$  to 25 years of age) in Study P301, there will be an at least 90% power to demonstrate

noninferiority of the immune response as measured by SRR in children at a 2-sided alpha of 0.05, compared with that in young adults  $\geq 18$  to 25 years of age in Study P301 receiving mRNA-1273, assuming SRR of 85% in young adults of  $\geq 18$  to 25 years of age from Study P301, true SRR of 85% in children (or true rate difference is 0 compared with young adults from Study P301), a noninferiority margin of 10% and a point estimate minimum threshold of -5% in SRR difference.

- In the 1273-P203 interim analysis (data snapshot on 08 May 2021), the observed seroresponse rates at Day 57 were high in both  $\geq 18$  to 25 years of age group from Study P301 (98.6% with 95% CI: 96.6, 99.6) and 12 to 17 years of age group (98.8% with 95% CI: 97.0, 99.7), based on pseudovirus nAb ID50 values. For this Study P204, if the true seroresponse rates were assumed to be 95% or higher in both  $\geq 18$  to 25 years of age group from Study P301 and an age group in children, with between-group true difference within 4%, there will be a >90% power to demonstrate noninferiority by seroresponse rate in children compared with  $\geq 18$  to 25 years of age in Study P301, at a 2-sided alpha of 0.05 and a noninferiority margin of 10%.
- Assuming approximately 25% of participants in the Immunogenicity Subset in Part 2 will not meet the criteria to be included in the PP Immunogenicity Subset, approximately 528 participants in Part 2 (~396 receiving mRNA-1273 and ~132 receiving placebo) will be selected for the Immunogenicity Subset from which approximately 289 participants on mRNA-1273 will be suitable for the PP Immunogenicity Subset in Part 2.
- In Part 1 or Part 2 for the booster dose primary immunogenicity analysis in an age group, with approximately 289 participants receiving mRNA-1273 booster dose in the PP Immunogenicity Subset with pre-booster negative SARS-CoV-2 in Study P204 and 289 young adults ( $\geq 18$  to 25 years of age) receiving mRNA-1273 100  $\mu$ g primary series in Study P301, there will be a 90% power to demonstrate noninferiority of the immune response, as measured by the antibody GM value, in children receiving a booster dose compared with that in adults ( $\geq 18$  to 25 years of age) receiving mRNA-1273 primary series in Study P301, at a 2-sided alpha of 0.05, assuming an underlying true GMR value of 1.0 and a noninferiority margin of 1.5. The standard deviation of the natural log-transformed GMT levels is assumed to be 1.5. Also, if the true SRRs were assumed to be 95% or higher in children receiving mRNA-1273 booster dose in Study P204 and adults receiving mRNA-

1273 primary series in Study P301, with between-group true difference within 4%, there will be a > 90% power to demonstrate noninferiority by SRR in children receiving a booster dose compared with adults receiving primary series in Study P301, at a 2-sided alpha of 0.05.

- In Part 3 for the primary series primary immunogenicity analysis, with approximately 289 participants receiving mRNA-1273 25 µg primary series in the PP Immunogenicity Subset in Study P204 and 289 adults ( $\geq 18$  years of age) receiving mRNA-1273 100 µg primary series in Study P301, there will be a 84% power to demonstrate noninferiority of the immune response, as measured by the antibody GM value, in children compared with that in adults ( $\geq 18$  years of age) receiving mRNA-1273 in Study P301, at a 2-sided alpha of 0.025, assuming a true GMR value of 1.0 and a noninferiority margin of 1.5. The standard deviation of the natural log-transformed GMT levels is assumed to be 1.5. Also, if the true SRRs were assumed to be 95% or higher in children in Study P204 and adults from Study P301, with between-group true difference within 4%, there will be a > 90% power to demonstrate noninferiority by SRR in children compared with adults in Study P301, at a 2-sided alpha of 0.025.
- In Part 3 for the third dose primary immunogenicity analysis, with approximately 289 participants receiving a third dose of mRNA-1273 dose in the PP Immunogenicity Subset with pre-third dose negative SARS-CoV-2 in Study P204 and 289 adults ( $\geq 18$  years of age) receiving mRNA-1273 100 µg primary series in Study P301, there will be a 84% power to demonstrate noninferiority of the immune response, as measured by the antibody GM value, in children receiving a third dose compared with that in adults ( $\geq 18$  years of age) receiving mRNA-1273 primary series in Study P301, at a 2-sided alpha of 0.025, assuming an underlying true GMR value of 1.0 and a noninferiority margin of 1.5. The standard deviation of the natural log-transformed GMT levels is assumed to be 1.5. Also, if the true SRRs were assumed to be 95% or higher in children receiving a third dose of mRNA-1273 dose in Study P204 and adults receiving mRNA-1273 primary series in Study P301, with between-group true difference within 4%, there will be a > 90% power to demonstrate noninferiority by SRR in children receiving a third dose compared with adults receiving primary series in Study P301, at a 2-sided alpha of 0.025.

Part 3 (Arm 14) was originally planned to enroll ~300 children aged 6 to <12 years to receive mRNA-1273 25 µg (2 doses of primary series and a third dose). However, arm 14 was closed to enrollment at an enrollment number of N = 91. All participants enrolled in Arm 14 will continue to be followed as per protocol, including receipt of third doses if not received yet, as well as immunogenicity samples.

Given that the number of participants enrolled in Part 3 (n=91) is substantially smaller than the planned sample size of ~300 required for the immunogenicity hypothesis testing after dose 2 of mRNA-1273 25 µg primary series and after a third dose of mRNA-1273 25 µg, the hypothesis testing will not be performed. Instead, all the analyses of immunogenicity endpoints will be descriptive.

Thus, the study objective of Part 3 was updated to evaluate descriptively safety and immune responses to 2 doses of mRNA-1273 25 µg primary series and a third dose of mRNA-1273 25 µg in 6 to <12 years of age. For the descriptive analysis purpose, the comparator will be young adults  $\geq 18$  to 25 years of age from P301, instead of  $\geq 18$  years of age, to be consistent with the comparator group in immunogenicity analyses in part 1 and part 2 of the study.

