The number and percentage of participants with seroresponse due to vaccination will be provided with 2-sided 95% CI using the Clopper-Pearson method at each post baseline time point with Day 57 being of the primary interest. The seroresponse rate difference with 95% CI using the Miettinen-Nurminen (score) confidence limits at Day 57 will be provided between children receiving mRNA-1273 in Study P204 and young adults of  $\geq 18$  to 25 years of age receiving mRNA-1273 from Study P301. For each pediatric age group, the noninferiority of seroresponse rate will be considered demonstrated if the lower bound of the 95% CI of the seroresponse rate difference is  $> -10\%$  based on the noninferiority margin of 10% and the seroresponse rate difference point estimate  $\geq -5\%$  (minimum threshold).

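### The >90% seroresponse power for true differences within 4 points omits the plan's own -5% point-estimate criterion; at 4 points the full rule gives about 77% to 81%

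*SAP*

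**What the plan says.** SAP section 4.2 (Part 1 open-label and Part 2 blinded phase) gives two power statements for the primary-series seroresponse rate (SRR).

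- **Base case, 85% in both groups.** At least 90% power, with the success conditions given as "a noninferiority margin of 10% and a point estimate minimum threshold of -5% in SRR difference".
- **High-rate case.** It applies "if the true seroresponse rates were assumed to be 95% or higher in both" the P301 young adults and a pediatric age group, and states that "with between-group true difference within 4%, there will be a >90% power to demonstrate noninferiority by seroresponse rate in children". The conditions attached are "at a 2-sided alpha of 0.05 and a noninferiority margin of 10" percent. The -5% threshold is not mentioned.

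Section 6.4.2 of the same plan sets the decision rule. The interval is specified as follows: "The seroresponse rate difference with 95% CI using the Miettinen-Nurminen (score) confidence limits at Day 57 will be provided". Noninferiority needs a lower 95% limit above -10% and an observed difference of at least -5%; the two conditions are joined in one sentence, "based on the noninferiority margin of 10% and the seroresponse rate difference point estimate".

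**The concern.** The high-rate statement claims power to demonstrate noninferiority but applies only half of the rule by which noninferiority is declared. The omitted half matters most in exactly this case. At a true difference of -4 points, the expected estimate lies one point from the -5% cut-off and six points from the margin. The point-estimate criterion should therefore set the power, yet the calculation leaves it out. This is not a convention of the document: the base-case SRR statement and the geometric mean (GM) statement next to it both name their point-estimate thresholds.

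SRR is one of two coprimary endpoints. Under the fixed sequence in section 6.4.2, both must succeed in an age group before alpha passes to the next. A reader who takes section 4.2 at its word would put the SRR failure risk below 10% anywhere within 4 points.

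**Working it through.** **Inputs**

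- Children: 289 per age group (section 4.2: "With approximately 289 participants receiving mRNA-1273 in the PP Immunogenicity Subset of each age group in Study P204 and young adults" of P301).
- Young adults: 289. This number is explicit for P301 only in the booster statement of section 4.2 and is the natural reading for the primary series; it is varied below.
- Two-sided alpha 0.05, margin 10 points (section 4.2).
- Interval: Miettinen-Nurminen score (section 6.4.2).
- Point-estimate criterion: observed difference at least -5% (section 6.4.2).
- True rates: both at least 95%, so the 4-point deficits run from 95% vs 99% to 96% vs 100% (children vs adults).

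**Method**

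With X ~ Bin(289, p_child) and Y ~ Bin(289, p_adult) independent, sum P(X = x)·P(Y = y) over all tables that meet the criterion:

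- margin alone: Miettinen-Nurminen lower 95% limit > -0.10;
- full rule: the same, and x/289 - y/289 ≥ -0.05.

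**Results**

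| Children vs adults | Margin alone | Full rule |
|---|---|---|
| 85% vs 85% (base case) | 91.6% | 91.6% |
| 95% vs 99% | 94.9% | 76.9% |
| 95.5% vs 99.5% | 96.4% | 79.0% |
| 96% vs 100% | 97.5% | 81.4% |
| 95% vs 98.6% (P301 rate quoted in section 4.2) | 96.5% | 83.6% |
| 95% vs 98.1% | 97.8% | 89.7% |
| 95% vs 98% | 98.0% | 90.6% |
| 95% vs 95% | 99.9% | 99.7% |

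The plan's own figures come first. The base-case claim of at least 90% is reproduced under the full rule. The high-rate claim of >90% is reproduced on the margin alone, but at 4 points it fails once the point-estimate criterion is applied.

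**Checks by hand**

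*95% vs 99%, normal approximation to the point-estimate criterion:*

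SE = √[(0.95×0.05 + 0.99×0.01)/289] = √(0.0574/289) = 0.0141

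P(estimate ≥ -0.05) = P(Z ≥ (-0.05 + 0.04)/0.0141) = P(Z ≥ -0.71) ≈ 0.76

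*96% vs 100%.* All adults respond, so the criterion depends on the children alone. It allows at most 14 non-responders, since 14/289 = 4.84% and 15/289 = 5.19%. P(Bin(289, 0.04) ≤ 14) = 0.814.

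In the rows with a deficit of 3 to 4 points, the full-rule probability equals the probability of meeting the point-estimate criterion. That criterion alone is binding there.

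**Sensitivity to the P301 group size.** With 200 to 350 young adults, the full rule gives 74.8% to 77.3% at 95% vs 99%. At 96% vs 100% the figure does not change.

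**The case against.** The strongest reply is that the sentence states its own conditions (alpha and the 10% margin) and that under them >90% is correct, 94.9% to 97.5% at the 4-point edge. That stands: the arithmetic is right for the criterion named, and the fault is an omission. But the sentence claims power to demonstrate noninferiority, and section 6.4.2 defines that with both criteria.

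Three further points limit the impact, and all stand.

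- **The shortfall sits at the edge of the range.** With adults at 98.6%, the full rule gives 98.9% for children at 96.6% and 92.5% at 95.6%. The rates quoted in section 4.2 (98.6% and 98.8%) suggest a difference near zero. Still, a claim for differences within 4 points includes the edge.
- **The sample size does not depend on this statement.** It rests on the GM and base-case SRR calculations, and the base case holds.
- **The tests have been run.** The multiplicity paragraph of the SAP for the Part 2 open-label phase, booster and Part 3 reports primary-series coprimary testing as completed and significant in all three age groups. Alpha has therefore already moved on.

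A joint coprimary figure is also open to objection. Multiplying by the 90.1% GM power gives 0.769 × 0.901 = 69% to 0.814 × 0.901 = 73%. This assumes independence, although both endpoints use the same Day 57 antibody values, and it pairs a 4-point SRR deficit with a true GMR of 1. It is illustrative only, and the conclusion does not rest on it.

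**Conclusion.** The concern holds. Under the plan's own success rule, the >90% claim fails at the 4-point end of its stated range: power is 76.9% to 81.4%, roughly 9 to 13 points below the 90% claimed. Across the stated rates it exceeds 90% only up to a deficit of about 3 points. This assumes about 289 per group, independent binomial outcomes and children having the lower rate; it is little affected by the P301 group size.

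The finding is confined to the primary-series high-rate statement. The 85%/85% statement is correct. The parallel booster statement is unaffected, because section 6.4.2 of the booster SAP has no point-estimate criterion. Part 3 hypothesis testing was dropped. With primary-series testing reported as complete, this corrects the record and changes no result.

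**What to change.** Restate the high-rate statement in section 4.2 under the full rule. For example: with true seroresponse rates of 95% or higher, power exceeds 90% if the true difference is within about 3 points; at 4 points it is about 77% (95% vs 99%) to 81% (96% vs 100%) because the observed difference must also be at least -5%. A smaller alternative is to keep the 4-point range and say explicitly that the >90% refers to the 10% margin criterion alone. Leave the booster statement as it is.

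The cost is one sentence and a slightly less favourable figure. Sample size, endpoints, decision rule and analyses do not change.
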